6.1.3. Safety Variables

Clinical safety will be evaluated by assessing treatment-emergent AEs, physical examinations, laboratory assessments, ECG, and vital signs results in a descriptive manner. Original results, changes and percent changes from baseline (or from screening, depending on the parameter) will be summarized for the laboratory data, vital signs, and ECG values. Values will be categorized as low/normal/high according to normal ranges, and shift tables versus baseline will be created to determine treatment-emergent abnormalities.

The analysis will present the results in 2 chapters:

1. Chapter 1: Analysis of the first study period, up to and including the Week 12 visit.
2. Chapter 2: Analysis of the full 24 weeks study period.

Subjects from the placebo and lowest dose group who are re-randomized at Week 12: the actual treatments will be presented. (See also: overview table, section 2.1.)

6.1.4. Pharmacokinetic Analyses

This will be elaborated in a separate SAP by [REDACTED].

6.1.5. Pharmacodynamic Analyses

Serum levels of YKL-40 will be described as actual values, changes from baseline and percent changes from baseline. Between-group comparisons will be performed using the same ANCOVA models as used for the efficacy data. To further explore the data, scatterplots of the percent change from baseline in YKL-40 values versus efficacy parameters will be created.

Further analyses may be done at a later time, but these will not be part of the CSR.

6.1.6. Pharmacokinetic, Efficacy, Safety and Pharmacodynamic Correlations

This will be elaborated in a separate SAP by [REDACTED].

6.2. INTERIM ANALYSIS

Note that a DSMB is installed to monitor unblinded safety data during the course of the study. This is described in a separate DSMB Charter and DSMB SAP.

An unblinded interim analysis will be performed when all subjects have reached Week 12 (or have discontinued before Week 12). Only data from this study period will be included in the interim analysis.

The analysis will not present everything, but only a selection of parameters:

- General: region and county distribution, trial termination reasons, demographics and baseline disease characteristics.
- Efficacy: ACR20/50/70, ACR-N, SDAI and CDAI, DAS28(CRP), the ACR components (joint counts, CRP, HAQ-DI and the 3 VAS scores).
- Safety: adverse events, laboratory safety and vital signs.

The exact tables and figures to be produced for this interim analysis are identified in the next sections where all the TLFs are defined. The interim analysis is intended to support preliminary dose selection for the GLPG0634 phase III program.

Because this efficacy analysis consists of parts of the full Week 12 primary analysis, there is no inflation of the type-I error rate, and therefore no statistical correction is applied.

To preserve the blind for Team members who have access to raw patient data, the following approach will be used:

The statistical analysis of the unblinded data will be handled by a statistician at [REDACTED] who is independent from the regular study team. The regular study team (including [REDACTED] lead statistician and corresponding [REDACTED] biometrics team) will remain blinded.

This interim analysis output will comprise summary tables and plots, but no listings. These summary results will be viewed by the sponsor, but no individual subject data (such as listings or datasets) will be exchanged.

To prevent accidental unblinding of specific subjects, the following rules will also be applied:

- For descriptive statistics: min-max lines will be suppressed.
- For frequency tables containing small numbers of subjects in some categories (e.g., trial termination reasons, demographics/baseline characteristics, AEs & SAEs, and lab & vital signs abnormalities), the following rules will be programmed in the tables:
 - If there are events in multiple groups, including the placebo group: the full details will be shown in the table, per treatment group. This does not cause any unblinding of specific subjects.
 - If there are events in only one of the groups (either a GLPG0634 dose group or the placebo group): this would unblind these subjects. To prevent this, the individual groups will be left blank in the frequency table, and only the “overall total” group will be populated.
 - If there are events in multiple groups, but none in the placebo group: this would partially unblind these subjects, indicating that all of them received GLPG0634. To prevent this, the individual groups will be left blank in the frequency table, and only the “overall total” group will be populated.

The analysis TLFs will be checked for potential unblinding details by the [REDACTED] independent statistician prior to delivery to the sponsor.

6.3. CHANGES TO THE PLANNED ANALYSES, NOT COVERED BY PROTOCOL AMENDMENTS

6.3.1. Changes before Interim Database Lock

No changes to the protocol-specified analyses were made. The SAP provides further elaborations, clarifications and specifications on the protocol-specified analyses.

6.3.2. Changes after Interim Database Lock but before Final Database Lock

Changes from 1.0 to 2.0 SAP:

Corrections:

- The analysis periods were updated from the interim SAP: the actual Week 12 visit date day is now included in the first 12 weeks of the study period. In the interim SAP it was mistakenly excluded from the first 12 weeks of the study.
- Randomization stratification factors: it is now more clearly specified that in case of discrepancies between IWRS and eCRF, the real underlying eCRF stratum will be used in the analyses and analysis models. This was already so in the interim analysis, but possibly not clear enough in this SAP.
- For safety data, the overall total was replaced by a total across the GLPG0634 groups only. This will allow easier comparison of the overall GLPG0634 safety versus the placebo group.
- Baseline HAQ-DI, Baseline SDAI and Baseline CDAI will be added in the table on baseline disease characteristics.
- VAS plots on percent changes from baseline: from the interim analysis it seemed that the mean values were not so much influenced by the few outliers as initially anticipated. Therefore medians are no longer needed: plots will be mean plots just like all other efficacy parameters.
- Scatterplots between PK plasma levels and safety (lab safety and ECG QTcF) were removed. Because PK plasma sampling can happen at any time relative to the last drug intake ('sparse sampling'), the result is not always representing the subject's exposure. Making a correlation between the PK finding and safety would then be misleading.

Additions:

- Pharmacodynamic analyses were added and specified for the final analysis.
- DAS28(CRP) remission and low disease activity, CDAI remission, SDAI remission: between-group inferential statistics were added, similar to the ACR20 analysis, to allow a more detailed interpretation of the results.

6.3.3. Changes after Final Database Lock

None.

7. DEFINITIONS OF GENERAL TABLES, LISTINGS AND FIGURES

Mock tables, listings and figures are provided in a separate document.

All analyses will be run on the Safety population, unless specified otherwise.

7.1. SUBJECT DISPOSITION

Listing 16.2.1.1: Subject disposition: Randomization

Listing of subject numbers, randomization and re-randomization groups, population flags, any information on code breaking, stratification factors (region, previous use of biologics), country and site.

All discrepancies (as-randomized versus as-treated, or discrepancies in stratification factors) will be flagged.

Regions used in the central randomization in the DARWIN program are:

Region	Countries belonging to the region
1: Latin America	Argentina, Chile, Colombia, Guatemala, Mexico
2: Central and Eastern Europe, EU	Bulgaria, Hungary, Latvia, Poland, Romania
3: Central and Eastern Europe, non-EU	Russia, Ukraine, Moldova
4: West and Asia Pac	Australia, Austria, Czech Republic, Germany, New Zealand, Spain, USA

Population: all randomized population.

Listing 16.2.1.2: Subject disposition: Region, country and site identification

Listing of region, country and site numeric codes used for the numbering of the subjects, and the meaning of these codes.

Population: all screened population.

Table 14.1.1.1: Subject disposition: Tabulation by region, country and investigator

Tabulation per initial treatment group (and overall) of the number of subjects in each of the regions, countries and investigator sites. For the interim analysis, only regions and countries will be presented.

Population: all randomized.

Table to be created for the Week 12 interim analysis as well.

Table 14.1.1.2: Subject disposition: Analysis populations

Tabulation per initial treatment group (and overall) of the number of subjects in each of the analysis populations defined in section 3.1, separated per study period.

Population: all screened population.

Table 14.1.1.3: Subject disposition: No-treatment subjects: Tabulation of the reasons

Tabulation of discontinuations and the reasons for discontinuation.

Population: all screened population, minus the safety population (so selecting only subjects who were never exposed to the study medication: subjects either never randomized or randomized but not exposed).

Table 14.1.1.4: Subject disposition up to Week 12: Tabulation of the number of subject at each time interval

Tabulation per treatment group (and overall) and per time point (up to and including Week 12).

Population: safety.

Table 14.1.1.5: Subject disposition up to study end: Tabulation of the number of subject at each time interval

Repeat table after Week 12 and follow-up.

Population: safety subjects who entered the second part of the study.

Listing 16.2.1.3: Subject disposition: Number of days in study

Listing per initial treatment group, per subject and per time point the number of days in study at the time of the visit (derivation of these “days”: see section 3.1), with population flags.

Population: safety.

Table 14.1.1.6: Subject disposition: First and last date in the study

List the following (overall, not per subject):

- Date of the first signature on study ICF
- Date of first and last screening visit
- Screening period duration: last screening date – first screening date + 1 day
- Date of first study drug administration (periods 1 and 2)
- Last visit date (all visits; including unscheduled visits)
- Last date of contact in the study with any subject.

Population: all screened population.

Table 14.1.1.7: Subject disposition up to Week 12: Tabulation of the trial termination reasons

Tabulation per treatment group (and overall) of completion/discontinuations during the first period of the study, with the reasons for discontinuation. Subjects who moved on past the Week 12 visit will be shown as “completed”.

Population: safety.

Table to be created for the Week 12 interim analysis as well.

Table 14.1.1.8: Subject disposition up to study end: Tabulation of the trial termination reasons

Repeat table for the second period of the study.

Population: safety subjects who entered the second part of the study.

Listing 16.2.1.4: Subject disposition: Trial termination

Listing per treatment group and per subject of the reason for completion/discontinuation and the number of days since first study treatment administration at trial termination. In case the discontinuation was due to AE, the AE preferred term will be presented in this listing. If there is a (verbatim) explanation on the discontinuation reason, this will also be presented in this listing.

Population: safety.

Listing 16.2.1.5: Subject disposition: Study analysis periods

Listing per treatment group and per subject of the analysis periods in the study, together with the start and end dates of each analysis period. With the date of first and last use of study medication in each study period, population flags, the ICF signature date and trial termination date. (Analysis periods: see section 3.2)

Population: safety.

7.2. PROTOCOL DEVIATIONS AND ELIGIBILITY

Protocol deviations are determined and recorded whilst the study is ongoing, and the list is finalized prior to database lock (and unblinding). All deviations are classified as either “critical” or “non-critical”. Only the critical (=major) protocol deviations will be presented in the tables. For more details, please refer to the Protocol Deviation Plan.

Table 14.1.2.1: Major protocol deviations

Tabulation per treatment group (and overall) of the number (and percentage) of subjects having a major/minor protocol deviation, together with the detailed protocol deviation categories of the major deviations only.

Population: safety.

Listing 16.2.2.1: Protocol deviations

Listing per treatment group and per subject of all protocol deviations, with indication critical/non-critical.

Population: safety.

Listing 16.2.2.2: Eligibility criteria: Violations

Only violated in- and exclusion criteria will be listed per treatment group and per subject. These are criteria as ticked by the investigator in the eCRF.

Population: safety.

Listing 16.2.2.3: Final eligibility statements

Listing per treatment group and per subject of the final eligibility statements in the eCRF at screening and at baseline.

Population: safety.

7.3. SUBJECTS EXCLUDED FROM ANALYSIS**Listing 16.2.3.1: Subjects excluded from the safety analysis**

Listing of all subjects that were randomized and/or not treated: the trial termination reason and/or the reason for being a no-treatment subject will be listed, whichever is available.

Population: all screened population, minus the Safety population.

Listing 16.2.3.2: Subjects excluded from the efficacy ITT analysis

Listing of all subjects that were exposed but who were not included in the ITT population: the trial termination reason and the reason for being excluded will be listed.

Population: Safety, minus the ITT population.

Listing 16.2.3.3: Subjects excluded from the efficacy per-protocol analysis

Listing of all subjects that were in the ITT population but not in the per-protocol population: the trial termination reason and the reason for being excluded will be listed.

Population: ITT population, minus the Per-protocol population.

7.4. DEMOGRAPHICS AND BASELINE DISEASE CHARACTERISTICS

7.4.1. Parameters

- sex
- age (years) as recorded in the eCRF
- age categories:
 - < 45 ;
 - [45,65[;
 - [65,75[;
 - ≥ 75 years
- year of birth: only listed
- race
- ethnicity
- height (cm)
- weight (kg)
- body mass index BMI = (weight in kg) / (height in m)² (kg/m²): the BMI will be recalculated and rounded to the nearest integer, even when already available in the database. The original BMI will not be used in that case.
- BMI categories:
 - ≤18.5;
 -]18.5,25.0] ;
 -]25.0,30.0[;
 - ≥30.0 kg/m²

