#### **8.3.2 Inclusion Criteria**

To be eligible for study entry subjects must fulfil all of the following criteria:

1. Male or female subjects who are  $\geq 18$  years of age on the day of signing informed consent.
2. Diagnosis of RA since at least 6 months prior to Screening and meeting the 2010 ACR/EULAR criteria of RA and ACR functional class I-III.
3. Have  $\geq 6$  swollen joints (from a 66-joint count) and  $\geq 8$  tender joints (from a 68-joint count) at Screening and Baseline.
4. Screening serum CRP  $\geq 0.7$  x upper limit of the normal (reference) laboratory range (ULN).
5. Have shown an inadequate response in terms of either lack of efficacy or toxicity to MTX.
6. Have agreed to be washed out from MTX for a period of at least 4 weeks before or during the Screening period.
7. If taking oral steroids, these should be at a dose  $\leq 10$  mg/day of prednisone or prednisone equivalent and stable for at least 4 weeks prior to Baseline.
8. If taking non-steroidal anti-inflammatory drugs (NSAIDs), these must be at a stable dose for at least 2 weeks prior to Baseline.
9. The results of the following laboratory tests performed at the central laboratory at Screening must be within the limits specified below:
  - a) Hemoglobin  $\geq 10$  g/dL (International System of Units [SI]:  $\geq 100$  g/L);
  - b) WBCs  $\geq 3.0 \times 10^3$  cells/mm^3 (SI:  $\geq 3.0 \times 10^9$  cells/L);
  - c) Neutrophils  $\geq 2.0 \times 10^3$  cells/mm^3 (SI:  $\geq 2.0 \times 10^9$  cells/L);
  - d) Lymphocytes  $\geq 1.0 \times 10^3$  cells/mm^3 (SI:  $\geq 1.0 \times 10^9$  cells/L);
  - e) Platelets  $\geq 100 \times 10^3$  cells/mm^3 (SI:  $\geq 100 \times 10^9$  cells/L);
  - f) Serum ALT and aspartate aminotransferase (AST)  $\leq 1.5$  x ULN;
  - g) Total bilirubin level  $\leq 1.25$  x ULN;
  - h) Alkaline phosphatase  $\leq 1.5$ ULN;
  - i) Lipase  $\leq 1.5$  x ULN and amylase  $\leq 1.5$  x ULN;
  - j) Creatinine clearance  $>60$  mL/min. Creatinine clearance will be calculated using the Cockcroft-Gault formula.
10. Female subjects must have a negative pregnancy test unless they are surgically sterile or have been post-menopausal for at least one year (12 consecutive months without menses); in case of doubt a determination of serum FSH can be done with FSH levels above 35 mIU/mL being confirmative for menopause.

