7.5. BASELINE DISEASE CHARACTERISTICS

7.5.1. Parameters

- Duration of RA (years) = $\frac{(\text{date of initial diagnosis}) - (\text{screening date}) + 1}{365.25}$, rounded to the nearest integer. If the date of initial diagnosis is incomplete, then the following rules will be applied: Missing day: use the first of the month. Missing month: use January.
- Duration of RA, categorized:
 - <0.5;
 - [0.5,2[;
 - [2,5[;

- [5,10[;
- [10,20[;
- ≥20 years
- Screening and baseline CRP
- Screening and baseline CRP, categorized:
 - <0.7 x ULN;
 - [0.7,1.0] x ULN;
 -]1.0,1.2[x ULN;
 - ≥ 1.2 x ULN
- Change in CRP (baseline – screening)
- Screening and baseline TJC68 and SJC66
- Change in TJC68 and SJC66 = baseline – screening
- Screening and baseline DAS28(CRP) – see further sections for the definition of the DAS28(CRP)
- Change in DAS28(CRP) = baseline – screening
- Screening and baseline patient’s global evaluation of disease activity (0-100 mm VAS)
- Change in patient’s global evaluation of disease activity = baseline – screening
- Baseline investigator’s global evaluation of disease activity (0-100 mm VAS)
- Baseline patient’s pain score (0-100 mm VAS)
- Baseline HAQ-DI
- Baseline SDAI
- Baseline CDAI
- RF status, classified as positive/negative based on the upper limit of the normal range (ULN):
 - o Positive: value > ULN
 - o Negative: < value ≤ ULN
 - o Missing: value is missing for any reason.
- Anti-CCP status, classified as positive/negative based on the upper limit of the normal range (ULN):
 - o Positive: value > ULN
 - o Negative: < value ≤ ULN
 - o Missing: value is missing for any reason.
- Affected joints identification
- Prior RA medication:
 - o Generic names, also classified as: biological (anti-TNF or other biological DMARD), anti-TNF, other biological DMARD, conventional DMARD, NSAID, steroid, analgesic, other RA medication.
 - o MTX duration (study screening date – date of start of MTX + 1 day), expressed in years. If there were multiple dosing periods of MTX, then the “duration” will add up all such episodes.
 - o MTX duration, categorized as:
 - <0.5;
 - [0.5,2[;
 - [2,5[;
 - [5,10[;

- [10,20[;
- ≥20 years
- Steroids (as prednisolone-equivalent): total daily dose at the start of the study
- Steroids (as prednisolone-equivalent): total daily dose at the start of the study, categorized as:
 - <5 ;
 - [5,10[;
 - [10,15[;
 - [15,20[;
 - ≥20 mg/day.

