Table to be created for the Week 12 interim analysis as well, cut off at Week 12. ITT only.

Table 14.2.1.1.3: ACR50: Summary with overall p-value and pairwise comparisons versus placebo

Repeat table of the ACR20 table.

The table will show:

- NRI in ITT

- LOCF in ITT
- observed-case in ITT (descriptive at Week 12 + 24; inferential statistics at Week 12 only).

Table to be created for the Week 12 interim analysis as well, cut off at Week 12.

Table 14.2.1.1.4: ACR50: Exploratory pairwise comparisons among the dose groups

Repeat table of the ACR20 table.

The table will show:

- NRI in ITT
- LOCF in ITT
- observed-case in ITT (inferential statistics at Week 12 only).

Table to be created for the Week 12 interim analysis as well, cut off at Week 12.

Table 14.2.1.1.5: ACR70: Summary with overall p-value and pairwise comparisons versus placebo

Repeat table of the ACR20 table.

The table will show:

- NRI in ITT
- LOCF in ITT
- observed-case in ITT (descriptive at Week 12 + 24; inferential statistics at Week 12 only).

Table to be created for the Week 12 interim analysis as well, cut off at Week 12.

Table 14.2.1.1.6: ACR70: Exploratory pairwise comparisons among the dose groups

Repeat table of the ACR20 table.

The table will show:

- NRI in ITT
- LOCF in ITT
- observed-case in ITT (inferential statistics at Week 12 only).

Table to be created for the Week 12 interim analysis as well, cut off at Week 12.

Table 14.2.1.1.7: ACR20 at Week 12: Tabulation versus baseline characteristics

The table will show two methods of imputing missing values: LOCF and NRI.

Frequency tabulation of the ACR20 response rate at Week 12 per treatment group, split up according to the following baseline categories:

- Demographics:
 - Region (as used in the central randomization)

- Country
- Gender
- Age categories:
 - < 45 ;
 - [45,65[;
 - [65,75[;
 - ≥ 75 years
- BMI categories:
 - ≤ 18.5;
 -] 18.5 , 25.0] ;
 -] 25 , 30 [,
 - ≥ 30 kg/m²
- Baseline disease characteristics:
 - Duration of RA:
 - < 1;
 - [1 , 2 [;
 - [2 , 5 [;
 - [5 , 10 [;
 - [10 , 20 [;
 - ≥ 20 years
 - Baseline CRP:
 - <0.7 x ULN;
 - [0.7,1.0] x ULN;
 -]1.0,1.2[x ULN;
 - ≥ 1.2 x ULN
 - Baseline TJC68: < 20, ≥ 20
 - Baseline SJC66: < 20, ≥ 20
 - Baseline DAS28(CRP): high, moderate, low, remission (see further section on DAS28 for the definition of these categories)
 - RF status
 - Anti-CCP status
 - Previous use of:
 - Biological DMARD (anti-TNF or other biological DMARD) yes/no,
 - anti-TNF yes/no,

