12.2.3. Number of Significant Digits

The original results and normal limits will be rounded to present only a relevant number of digits. The Mock TLFs contains a table on the expected number of significant digits per lab test. This rounding will be done prior to any parameter derivation. Note that this table also contains the classification of lab tests into categories.

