12.3.2. Calculated Parameters

The QTc will always be derived during the statistical analysis, even when already available in the database. The value in the database will not be used in the analysis.

The QTc will be calculated using the following formula: Fridericia's cube-root corrected QT (Fridericia, 1920):

$$QTcF \text{ (ms)} = QT \text{ (ms)} \times \sqrt[3]{\frac{HR(bpm)}{60}}$$

The QTcF will be rounded up to the nearest integer prior to the derivation of changes and categorizations.

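### BMI and RA duration are defined only as whole numbers but classed at limits that do not suit integers, so baseline and subgroup tables can misplace subjects and the under-1-year RA class is essentially empty

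*SAP*

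**What the plan says.** - **BMI, SAP 7.4.1.** BMI is weight over height squared; "the BMI will be recalculated and rounded to the nearest integer, even when already available in the database". The section adds: "The original BMI will not be used in that case". The classes follow directly: ≤18.5; ]18.5, 25.0]; ]25.0, 30.0[; ≥30.0 kg/m².
- **RA duration, SAP 7.5.1.** Duration is in years, "rounded to the nearest integer. If the date of initial diagnosis is incomplete, then the following rules will be applied". The next item, "Duration of RA, categorized", lists <0.5; [0.5, 2[; [2, 5[; [5, 10[; [10, 20[; ≥20. Methotrexate duration in the same section has the same limits and no rounding.
- **Subgroup tables.** Table 14.2.1.1.7 (SAP 8.1.2) is described as: "Frequency tabulation of the ACR20 response rate at Week 12 per treatment group, split up according to the following baseline categories". Its RA-duration classes start differently: <1; [1, 2[; then [2, 5[ and upward. Table 14.2.1.4.6 (SAP 8.4.2) uses the same set for the DAS28(CRP) change.
- **Entry rule, Protocol 8.3.2.** "Diagnosis of RA since at least 6 months prior to Screening".
- **Order of rounding elsewhere.** SAP 12.3.2: "The QTcF will be rounded up to the nearest integer prior to the derivation of changes and categorizations". SAP 12.2.3, on laboratory results and normal limits: "This rounding will be done prior to any parameter derivation".

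**The concern.** Classes should be cut from the most precise value available. Here the integer is the only BMI and the only RA duration that the SAP defines, while several limits (18.5 kg/m², 0.5 year) make sense only for fractional values. A programmer who follows the text will class the integer. Subjects close to a limit then land in a neighbouring class, and for RA duration the shift is always upward.

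At stake are class counts in the baseline tables and response rates by class in the two subgroup tables. Several of these are also interim outputs: Tables 14.1.3.1, 14.1.3.2, 14.1.3.7 to 14.1.3.9 and 14.2.1.1.7. SAP 6.2 says that the interim analysis supports preliminary phase III dose selection.

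**Working it through.** The documents give no misclassification figure and no distribution of BMI or RA duration, so there is no stated number to reproduce. The check has two parts: which values change class, which needs no assumption about the distribution, and how many subjects that may be, which does.

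**1. Values that change class if the integer is classed**

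| Variable and table | True values misplaced | Where they go |
|---|---|---|
| BMI | above 25.0 to below 25.5 | ]18.5, 25.0] |
| BMI | 29.5 to below 30 | ≥30 |
| RA duration, subgroup tables | 0.5-1, 1.5-2, 4.5-5, 9.5-10, 19.5-20 y (upper end excluded) | next class up |
| RA duration, baseline table | 1.5-2, 4.5-5, 9.5-10, 19.5-20 y (upper end excluded) | next class up |

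The BMI class ]25.0, 30.0[ can hold only the integers 26 to 29, that is, true values from 25.5 to below 29.5: 4 of its 5 units. The 18.5 limit is harmless except for a value of exactly 18.5. The subgroup class [1, 2[ holds only the integer 1, that is, true values from 0.5 to below 1.5 years. In the baseline table, 0.5 to below 1 year rounds to 1 and stays correctly in [0.5, 2[.

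**2. The <1 year class.** Only a duration below 0.5 year rounds to 0, and the entry rule excludes almost all of these. One edge case remains: 181 days gives (181 + 1)/365.25 = 0.498, which rounds to 0. The printed formula in SAP 7.5.1 subtracts the screening date from the diagnosis date. I treat that as a sign slip, separate from this point, and use screening minus diagnosis plus 1.

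**3. BMI share (distribution assumed).** Share = P(25 < X < 25.5) + P(29.5 < X < 30).
- N(27, 5): [Φ(-0.3) - Φ(-0.4)] + [Φ(0.6) - Φ(0.5)] = 3.75% + 3.43% = 7.2%, about 20 of 280.
- N(26, 4.5): 7.5%. N(28, 6): 6.2%.
- Normal and lognormal, mean 24-30, SD 4-7: 4.2% to 8.6%.

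**4. RA-duration share (distribution assumed).** Take 0.5 year plus an exponential with mean 7.5, so an overall mean of 8 years. The mass in the half year below limit *a* is exp(-(a-1)/7.5) × (1 - exp(-0.5/7.5)):
- a = 1: 6.45%
- a = 2: 5.64%
- a = 5: 3.78%
- a = 10: 1.94%
- a = 20: 0.51%

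Subgroup tables: the sum is 18.3%, about 51 of 280. Baseline table, without a = 1: 11.9%, about 33 of 280. The 6.45% at a = 1, about 18 of 280, are the subjects who belong in <1 and are counted in [1, 2[.

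The wider grid covers the shifted exponential, and gamma and lognormal distributions truncated at 0.5 year, with means of 5-12 years and, for gamma and lognormal, coefficients of variation of 0.7-1.2:
- Subgroup tables: 8.0% to 24.9%.
- Baseline table: 8.0% to 15.7%.
- True share under 1 year: 0% to 11.6%.

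**5. Exploratory models.** Tables 14.2.1.1.8 and 14.2.1.4.7 use both variables as continuous. Rounding to an integer adds variance of about 1/12 = 0.083: about 0.3% of the BMI variance at an SD of 5 (0.083/25) and about 0.1% of the duration variance at an SD of 8 (0.083/64). That is negligible.

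**The case against.** The strongest reply is that the SAP never says that BMI or RA-duration classes are cut from the rounded value. Where it wants rounding first, for QTcF and laboratory results, it says so. Limits such as 18.5 and 0.5 suggest that the authors had fractional values in mind. This stands in part: the order is an inference. It remains the natural reading, because no other value is defined, the database BMI is expressly set aside, methotrexate duration is left unrounded beside it, and rounding comes first wherever the SAP does state an order.

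The reply is also right on size and reach:
- Every percentage depends on an assumed distribution. A single narrow range for RA duration, such as 15-23%, reflects one family of distributions and does not carry over to the baseline table.
- The two subgroup tables are descriptive and have no test. Misplaced subjects move to an adjacent class and are not lost. Under the exponential example, the <1 class would hold only 4 or 5 subjects per arm (18/4).
- Diagnosis dates with a missing day or month are set to the first of the month or to January, so full precision is not available for everyone.

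A reader might also infer from SAP 12.2.3 that laboratory abnormalities are being missed. A value just above its limit could round to equality, and boundary values are scored normal under 12.2.5.1. Whether this can happen depends on the digits per test, which are in the separate Mock TLFs. If those match the reported precision, nothing changes. The documents support a request for clarification, not a claim of error.

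**Conclusion.** The point holds as a minor one. If the SAP text is followed in its natural reading, BMI and RA-duration classes are wrong near their limits. The direction and location of the errors are certain on that reading; the number of subjects is not. Under the stated assumptions:
- BMI: about 6-8% (mean 26-28, SD 4.5-6), or about 4-9% over the wider grid.
- RA duration: about 8-25% in Tables 14.2.1.1.7 and 14.2.1.4.6, and about 8-16% in the baseline table.
- The <1 year class of the two subgroup tables is essentially empty. It is not strictly impossible to fill, given the 181-day case and possible eligibility violations.

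A reader might go further and infer damage to the efficacy conclusions. The documents do not support that. The Week 12 ACR20 model uses treatment, region and previous use of biologics, and neither BMI nor RA duration enters it. The effect is confined to baseline and subgroup output, some of it also produced for the interim analysis.

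**What to change.** - In SAP 7.4.1 and 7.5.1, derive BMI and RA duration at full precision, assign classes and fit the exploratory models on the unrounded values, and round only what is displayed.
- Align the RA-duration classes of the baseline table with those of Tables 14.2.1.1.7 and 14.2.1.4.6, or say why they differ.
- In SAP 12.2.3, derive flags, grades and changes from the reported laboratory values and limits, and round only what is printed.
- SAP 6.3.2 shows that the interim analysis had already been run when version 2.0 was written. Check which rule its tables used, and record any change there.

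The cost is a few lines of SAP text and a change in derivation order, with a rerun of the affected tables if the integers were classed. No new data are needed.
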